### 5.4.1. As Observed Analysis

The "as observed" strategy is used in so-called "observed cases" or "completers" analysis ubiquitous in the literature. For this analysis, only data from completers at the visit are relevant. All efficacy data will be summarized using an "as observed" analysis and summaries based on observed data at each postbaseline visit will be provided.

### 5.4.2. Last Observation Carried Forward

In this analysis, all missing values will be imputed using last observation carried forward (LOCF). Baseline values will be used for imputation if there is no postbaseline observation.

# 5.4.3. Markov Chain Monte Carlo - Multiple Imputation (MCMC-MI)

The method of handling missing efficacy data relative to the supportive hybrid estimands for the primary and secondary endpoints at Week 16 will be based on Markov Chain Monte Carlo Multiple Imputation (MCMC-MI). For patients who discontinue treatment due to lack of efficacy prior to Week 16, set to the patient's baseline value subsequent to this time through Week 16. MCMC-MI will be used to handle the remaining missing data.

The method of handling missing efficacy data relative to the supportive hybrid estimand for secondary endpoints at Week 24 will be based on MCMC-MI. For patients who discontinue treatment due to lack of efficacy after Week 16, set to the patient's baseline value subsequent to this time through Week 24. MCMC-MI will be used to handle the remaining missing data. Imputation will be conducted within each treatment group independently so that the pattern of missing observations in one treatment group cannot influence missing value imputation in another.

For each imputation process, 25 datasets with imputations will be calculated. The initial seed values are given in Table KGBO.5.3. The response rates and their associated SEs will be computed for each data set using SAS PROC FREQ with the riskdiff option specified for the appropriate column in the TABLES statement. The response rates and SEs from the resulting output will be combined across the 25 imputed datasets using SAS PROC MIANALYZE.

For binary responses related to EASI and IGA, the binary response variables will be calculated based on the multiply imputed datasets that have been created. Because the MCMC algorithm is based on the multivariate normal model, imputed values for IGA will not generally be one of the discrete values used in IGA scoring (0, 1, 2, 3, or 4). Therefore, to derive the binary IGA response variable, standard rounding rules will be applied to the imputed values. For example, if a patient has an IGA score imputed as 1.4 (and assuming a baseline IGA score of 3), the imputed value would be rounded down to 1, and the minimum change from baseline of 2 would have been met. This patient would be considered a responder.

For derivation of an EASI-75 and EASI-90 response, no rounding will be performed. The imputed EASI value will be compared directly to the observed baseline EASI value to determine whether a reduction of at least 75% or 90% was achieved at each visit.

For derivation of the following Pruritus NRS, Skin Pain NRS, Sleep-Loss Scale, and DLQI responses, no rounding will be performed. The imputed Pruritus NRS, Skin Pain NRS, and Sleep-Loss Scale values will be compared directly to the observed mean baseline values to determine whether a response was achieved. The imputed DLQI values will be compared directly to the observed baseline values to determine whether a response was achieved.

- Proportion of patients with a Pruritus NRS of ≥3 points at baseline achieving at least a 3-point reduction by visit.
- Proportion of patients with a Pruritus NRS of ≥4 points at baseline achieving at least a 4point reduction by visit.
- Proportion of patients with a Skin Pain NRS of ≥4 points at baseline achieving at least a 4-point reduction by visit.
- Proportion of patients with a Sleep-Loss Scale of ≥2 points at baseline achieving at least a 2-point reduction by visit.
- Proportion of patients with DLQI of ≥4 points at baseline achieving at least a 4-point reduction by visit.

Note that the estimate and 90% confidence interval bounds output by this SAS PROC MIANALYZE are percents (i.e, they are in terms of the response rate). To obtain the number of responders, the estimated percent is multiplied by the number of individuals in the analysis population and rounded to the nearest integer.

Imputation of continuous data will parallel that of binary variables. IGA, EASI, Sleep-Loss, Skin Pain NRS, Pruritus NRS, DLQI, CDLQI, and SCORAD will be summarized using an MCMC-MI analysis.

Analysis	Seed Values for Weeks 0- 16 of the Treatment Period; LEB 250mg Q2W	Seed Values for Weeks 16- 24 of the Treatment Period; LEB 250mg Q2W or Q4W
Proportion of patients achieving IGA of 0 or 1 with $a \ge 2$ -point improvement from baseline by visit.	661769200	893745627
Percent change from baseline in EASI score by visit. EASI-75 and EASI-90 will leverage imputation from EASI and therefore use the same	153233047	345987238
seed numbers. Change from baseline in Pruritis NRS Score by visit. Proportion of patients with a Pruritus NRS Score of $\geq$ 3 or $\geq$ 4 points at baseline achieving at least a 3point or 4-point reduction will leverage imputation from Pruritis NRS Score and therefore	502899349	302781834
use the same seed numbers. Change from baseline in Sleep-Loss Scale by visit. Proportion of patients with a Sleep-Loss Scale of ≥2 points at baseline who achieve at least a 2-point reduction at each visit will leverage imputation from Sleep-Loss Scale and therefore use the same seed numbers.	691405299	999692612
Change from baseline in Skin Pain NRS from baseline by visit. Proportion of patients with a Pruritus NRS Score of ≥4 points at baseline achieving at least a 4-point reduction will leverage imputation from Pruritis NRS Score and therefore use the same seed numbers.	81969225	20532740
Change from baseline in DLQI by visit. Proportion of patients with DLQI $\geq$ 4 points at baseline achieving at least a 4-point reduction will leverage imputation from DLQI and therefore use the same seed numbers.	66350097	60458639
Change from baseline in CDLQI by visit.	93794487	34792746
Change from baseline in SCORAD by visit.	90372454	71154457

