#### 4.2. Determination of Sample Size

Based on available data, the anticipated EASI-75 response rate is approximately 50%. A total sample size of 120 enrolled participants will provide >95% probability that the half-width of the 2-sided 90% CI of the EASI-75 response rate is at most 10%.

Example point estimates for EASI-75 response rates and corresponding 2-sided 90% CIs based on the Wilson-Score method for a sample size of 120 participants are summarized in the table below. The CIs are provided as reference rather than a basis of any decision criteria.

Example Point Estimates	Lower Bound of 90% CI	Upper Bound of 90% CI
40%	32.9%	47.5%
45%	37.7%	52.5%
50%	42.6%	57.4%
55%	47.5%	62.3%
60%	52.5%	67.1%

Table KGBO.4.1 Estimated 90% CI with Sample Size of 120 Participants

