# 5.1.2. General Considerations for Analyses

All analyses will be descriptive. Frequencies, percentages, and 90% Wilson-Score CIs for percentages will be reported for discrete efficacy endpoints. Mean, standard deviation, minimum, Q1, median, Q3, maximum, and the number of participants will be reported for continuous

efficacy endpoints. AEs, discontinuation, and other categorical safety data will be summarized using frequencies and percentages. Continuous vital signs, body weight, and other continuous safety variables including laboratory variables will be summarized descriptively as well.

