## 5.11. Efficacy Analyses

Table KGBO.5.4 includes the description and derivation of the efficacy measures and endpoints.

For categorical parameters, the number and percentage of patients in each category will be presented, as well as a 90% Wilson-Score confidence interval for the percentage. For continuous parameters, descriptive statistics will include n (number of patients), mean, standard deviation, Q1, median, Q3, minimum, and maximum. These summaries will be provided for the data asobserved and after implementation of LOCF and MCMC-MI imputation as described in Sections 5.4.2 and 5.4.3.

The IGA, F-IGA, EASI, BSA, Pruritus NRS, Skin Pain NRS, and Sleep-Loss Scale will be reported by clinic visit.

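### After multiple imputation the SAP specifies two different 90% intervals for response rates, Wilson and PROC MIANALYZE, and does not say which one is reported

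*SAP*

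**What the plan says.** SAP 5.1.2 sets the general rule: "90% Wilson-Score CIs for percentages will be reported for discrete efficacy endpoints". Section 5.11 repeats it for categorical efficacy parameters, "as well as a 90% Wilson-Score confidence interval for the percentage", and says these summaries are produced as observed, after LOCF and after MCMC-MI. Section 5.12 says the same for health outcomes.

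Section 5.4.3 describes the MCMC-MI analysis differently. Each of 25 imputed datasets yields a response rate and its SE, obtained from "SAS PROC FREQ with the riskdiff option specified for the appropriate column in the TABLES statement". Then: "The response rates and SEs from the resulting output will be combined across the 25 imputed datasets using SAS PROC MIANALYZE". A later note in 5.4.3 refers to the 90% bounds that MIANALYZE outputs. For the responder count, "the estimated percent is multiplied by the number of individuals in the analysis population and rounded to the nearest integer".

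Section 4.3 puts every participant on one regimen until Week 16. From then on there are two dose groups, defined by Week 16 response. Table KGBO.5.2 assigns MCMC-MI to the supportive hybrid estimands only; the primary estimand is analysed as observed.

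**The concern.** MIANALYZE bounds have the form estimate ± t × SE. A Wilson interval is asymmetric and stays within 0-100%. One table cannot carry both as its 90% interval, and the SAP gives no rule for building a Wilson interval from pooled results. Two programmers could follow the SAP and produce different tables.

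Each literal reading has a weakness. The MIANALYZE bounds can pass 100% when the rate is high, and they collapse to zero width if every imputed dataset has all or no responders. A plain Wilson interval on the rounded count leaves out between-imputation variance.

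The study plans no tests, so an interval is the only stated measure of uncertainty around a rate. The hybrid estimand is also the only one whose rule counts discontinuation for lack of efficacy as failure.

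**Working it through.** **Inputs.** From the SAP: n = 120 and an anticipated EASI-75 rate of about 50% (4.2); two-sided 90% level, z = 1.645; 25 imputations (5.4.3). Assumed, because the documents give no figure: 10% missing; about 60 participants per Week 24 dose group (50% of 120); Week 24 rates of 90% and 95% in the responder group.

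**1. The plan's own table.** The Wilson interval is [p + z²/2n ± z√(p(1−p)/n + z²/4n²)] / (1 + z²/n). With n = 120:

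| Rate | Wilson | p ± z√(p(1−p)/n) (Wald) |
|---|---|---|
| 40% | 32.9-47.5 | 32.6-47.4 |
| 45% | 37.7-52.5 | 37.5-52.5 |
| 50% | 42.6-57.4 | 42.5-57.5 |
| 55% | 47.5-62.3 | 47.5-62.5 |
| 60% | 52.5-67.1 | 52.6-67.4 |

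The Wilson column matches all ten bounds in Table KGBO.4.1; the Wald column does not. The largest possible Wilson half-width at n = 120 is 7.4 points, so the statement about a half-width of at most 10% is also true.

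**2. Size at n = 120.** At 50% the two methods differ by 0.1 point at each end. At 80%, Wald is 74.0-86.0 and Wilson 73.4-85.3. At 90%, Wald is 85.5-94.5 and Wilson 84.6-93.7. Every difference is below 1 point.

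**3. Size at n = 60, complete data.** For 54/60, Wald is 83.6-96.4 and Wilson 81.8-94.7. For 57/60, Wald is 90.4-99.6 and Wilson 88.1-98.0. For 58/60 the Wald upper bound is 100.5%.

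**4. With imputation.** Let q be the pooled rate, W the average within-imputation variance (close to q(1−q)/n), B the between-imputation variance and m = 25. Then r = (1 + 1/m)B/W, and the total variance is T = W(1 + r). MIANALYZE gives q ± t√T. A matching Wilson-type interval uses q with n replaced by n/(1 + r).

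Example with n = 60, q = 0.946, r = 0.065:
- W ≈ 0.946 × 0.054 / 60 = 0.000851; T = 1.065 × 0.000851 = 0.000907; √T = 0.0301.
- Degrees of freedom are 24 × (1 + 1/0.065)² ≈ 6,440, so t ≈ 1.645. MIANALYZE gives 89.6-99.6.
- The effective size is 60/1.065 = 56.3. The Wilson-type interval is 87.3-97.8.

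At n = 60, q = 0.911, r = 0.069 the two are 84.8-97.3 and 82.8-95.6. At n = 120, q = 0.507, r = 0.079 they are 42.9-58.5 and 43.0-58.4.

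**5. Coverage.** Simulated with 25 imputations, 10% missing and 3,000 runs; nominal level 90%. This tests the pooling step, not the SAP's multivariate normal imputation model.

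| n, true rate | MIANALYZE | Wilson-type, n/(1 + r) | Plain Wilson on rounded count | MIANALYZE upper bound above 100% |
|---|---|---|---|---|
| 120, 50% | 89.5% | 90.0% | 89.7% | 0% |
| 60, 90% | 88.7% | 91.4% | 84.2% | 8.1% |
| 60, 95% | 84.6% | 92.8% | 84.5% | 47.0% |

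A separate recomputation put MIANALYZE at 84% for n = 60 and 95%, and plain Wilson at about 83% for n = 60 and 90%.

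**The case against.** The strongest reply is that the specific section governs. Section 5.11 refers to the imputation as described in 5.4.3, and 5.4.3 names the MIANALYZE bounds, so a sensible programmer would report those. No section tells anyone to compute a Wilson interval from the rounded count; rounding is used only to display a number of responders. On that reading the defect is a missing cross-reference. This is fair and is the main reason the point is minor. But 5.11 and 5.12 do promise Wilson intervals after MCMC-MI, and the MIANALYZE bounds still misbehave at high rates.

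The n = 60 cases may also match no planned table. The Week 24 estimand population is the whole Treatment Period II population. Imputation is by dose group, but 5.4.3 does not say that rates are reported by group. If they are pooled at roughly n = 120, step 2 applies. This objection stands, so the n = 60 figures are conditional.

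Some stronger readings are tempting but not supported:
- A reader might infer from RISKDIFF that the SE is that of a difference between two groups. Section 5.4.3 takes response rates and their own SEs. For 90% in 60 participants that SE is √(0.09/60) = 0.039. The SE of a difference from a 40% group of the same size would be √(0.09/60 + 0.24/60) = 0.074. The valid point is only that a two-row option does not fit one group.
- A reader might look to the roughly 12 adolescents for the worst case. No MCMC-MI interval for a binary endpoint is clearly planned there: 5.14 plans descriptive age subgroups of the primary endpoint, and the listed cDLQI secondary endpoint is a change score.
- Wilson is not the truth against which Wald is always wrong. With complete data at n = 25 and a 90% rate, exact coverage is 91.9% for Wald and 83.0% for Wilson.

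**Conclusion.** The inconsistency is in the text: 5.1.2, 5.11 and 5.12 cannot be met together with 5.4.3, and RISKDIFF does not fit the single group through Week 16. Its practical size is small. It is about 0.1 point for the planned Week 16 EASI-75 case, and under 1 point at n = 120 for rates of 80-90%.

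A material effect needs Week 24 reporting by dose group, with about 60 participants, rates of 90-95% and 10% missing, all of which are assumptions. There the MIANALYZE upper bound passes 100% in about 8% of runs at 90% and 47% at 95%. Its coverage is close to nominal at 90% but about 84% at 95%. Plain Wilson on the rounded count covers about 83-84% at 90%.

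The documents do not support saying that the trial's main result carries wrong error bars. The as-observed primary analysis and the LOCF analysis can use Wilson directly, no test or decision depends on the intervals, and only the supportive hybrid estimands are touched. Severity: minor.

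**What to change.** In 5.4.3, replace RISKDIFF with a one-sample binomial proportion and SE, computed within each group that is reported. Report a Wilson-type interval built from the pooled rate and an effective sample size n/(1 + r), where r is the relative increase in variance from missing data. Set r = 0 when every imputed dataset has 0% or 100% responders, since r is otherwise 0/0. Keep the rounded responder count for display only.

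In 5.1.2, 5.11 and 5.12, state that this is the interval given after MCMC-MI and that the ordinary Wilson interval applies to as-observed and LOCF results. Pooling on the logit scale is a less convenient alternative, because it is undefined for any imputed dataset at 0% or 100% and would need its own rule.

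The cost is a few sentences, a few lines of code and slightly different bounds.

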9.3.3. Secondary Endpoint(s)/Estimand(s) Analysis

Secondary endpoints outlined in the objective will be analyzed similarly to the primary endpoint of the primary estimand, that is, using all observed data. For categorical endpoints related to reaching a threshold, analyses will be evaluated in participants who satisfy baseline minimum value (for xx-point improvement, baseline value need to be $\geq xx$) in intent-to-treat set.

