#### 5.1.1. Analysis Populations

Analysis populations are defined in Table KGBO.5.1 along with the analyses they will be used to conduct. The number of patients included in each population will be summarized.

Population	Description	
All Entered Patients	All patients who signed informed consent. Patient flow will be summarized.	
Intent-to-Treat (ITT)	All enrolled patients according to their planned intervention. Unless otherwise	
Population	specified, efficacy and health outcomes analyses for Weeks 0 to 16 of the	
	Treatment Period will be conducted on this population.	
Safety Population	All enrolled patients who received at least 1 confirmed dose of lebrikizumab	
	250 mg. Safety analyses will be conducted on this population.	
Treatment Period II	All enrolled patients who received at least 1 confirmed dose of lebrikizumab	
Population	250 mg during Weeks 16 to 24 of the Treatment Period. Unless otherwise	
	specified, efficacy and health outcomes analyses for Weeks 16 to 24 of the	
	Treatment Period will be conducted on this population. Additional efficacy	
	analyses for Weeks 0 to 24 of the Treatment Period may also be conducted on	
	this population.	

Table KGBO.5.1. Analysis Populations

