  - a. For participants who discontinue treatment prior to Week 16, a hypothetical strategy will be used to estimate what the treatment effect would have been if all subjects continued with treatment. Therefore, a hypothetical strategy is used for this type of ICE.
- D. Population-level summary: percentage of participants achieving EASI-75 response at Week 16.

## 5.2.3. Estimands for Secondary Endpoints at Week 16

The primary estimand for the primary endpoint will be applied to all secondary endpoints at Week 16. The supportive estimands for the primary endpoint will also be applied to all secondary endpoints at Week 16.

## 5.2.4. Estimands for Secondary Endpoints at Week 24

The primary estimand for the primary endpoint will be applied to all secondary endpoints at Week 24. There are two supportive estimands for secondary endpoints at Week 24. The first is a hybrid estimand representing the following clinical question of interest: What is the intervention effect in successful responses or means after 24 weeks of lebrikizumab intervention in participants with moderate-to-severe AD who have been previously treated with dupilumab if all participants adhered to treatment except those who discontinued due to lack of efficacy?

This estimand is described by the following attributes:

- A. Population: Treatment Period II population as described in Section 5.1.1.
- B. Endpoint: apply to all secondary endpoints at Week 24.
- C. Intercurrent events (ICEs): One ICE, permanent treatment discontinuation, is considered by this estimand as follows:
  - a. Participants who discontinue treatment due to lack of efficacy after Week 16 will be considered as treatment failures, i.e. non-responders, after the ICE. Therefore, a composite strategy is used for this type of ICE.
  - b. For participants who discontinue treatment due to reasons other than lack of efficacy after Week 16, a hypothetical strategy will be used to estimate what the treatment effect would have been if subjects continued with treatment. Therefore, a hypothetical strategy is used for this type of ICE.
- D. Population-level summary: percentage of successful responses or means at Week 24.

The second supportive estimand for secondary endpoints at Week 24 is a hypothetical estimand representing the following clinical question of interest: What is the intervention effect in successful responses or means after 24 weeks of lebrikizumab 250 mg Q2W intervention in

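### Read literally, the SAP's rule for MCMC-MI responder counts overstates the count for five secondary endpoints restricted by a baseline threshold

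*SAP*

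**What the plan says.** SAP 5.4.3 computes response rates and standard errors in each of 25 imputed data sets and pools them with PROC MIANALYZE. The pooled result is a percentage, so the SAP adds a rule for the number of responders: "the estimated percent is multiplied by the number of individuals in the analysis population and rounded to the nearest integer". The rule has no exception. It comes just after a list of five responder endpoints that are each confined to participants at or above a baseline value: Pruritus NRS (cut-offs 3 and 4), Skin Pain NRS (4), Sleep-Loss Scale (2) and DLQI (4).

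The SAP uses analysis population as a defined term. Section 5.1.1 states: "Analysis populations are defined in Table KGBO.5.1 along with the analyses they will be used to conduct". That table lists All Entered Patients, ITT, Safety and Treatment Period II. ITT is described as "All enrolled patients according to their planned intervention". Table KGBO.5.2 assigns the MCMC-MI analyses to ITT at Week 16 and to Treatment Period II at Week 24. SAP 5.2.4 repeats the latter: "Population: Treatment Period II population as described in Section 5.1.1".

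Protocol 9.3.3 says that for threshold endpoints "analyses will be evaluated in participants who satisfy baseline minimum value", within the intent-to-treat set. The objectives tables in both documents limit DLQI to those aged 16 or over at baseline. SAP 5.11 and 5.12 require both a number and a percentage after MCMC-MI imputation, so the derived count will appear in tables.

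**The concern.** A percentage computed among n participants gives a number of responders only when it is multiplied by n. If it is multiplied by a larger N, the product includes responders among people the endpoint never evaluated.

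Participants outside the denominator are to be expected:

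- The inclusion criteria (Protocol 5.1) set baseline minimums for EASI, IGA and BSA, but none for itch, skin pain, sleep loss or DLQI.
- Under SAP 5.1.2, a diary baseline with 3 or fewer responses in the week is missing, so that participant cannot be shown to meet a threshold.
- Participants under 16 complete the cDLQI and not the DLQI.

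At stake is the internal consistency of the MCMC-MI tables for these five endpoints at Weeks 16 and 24. The number of responders would not match the percentage and the denominator on which that percentage rests.

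**Working it through.** **The plan's own figures.** The plan states no responder count for any threshold endpoint. What can be recomputed is the precision table in SAP 4.2, which fixes N: "A total sample size of 120 enrolled participants will provide >95% probability" of the stated half-width. The Wilson interval has centre (p + z²/2N)/(1 + z²/N) and half-width z·√[p(1−p)/N + z²/4N²]/(1 + z²/N). With z = 1.645 and N = 120 it gives:

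- 40%: 32.9 to 47.5
- 45%: 37.7 to 52.5
- 50%: 42.6 to 57.4
- 55%: 47.5 to 62.3
- 60%: 52.5 to 67.1

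All five rows agree with the SAP. The largest half-width at N = 120 is 7.4%, inside the stated 10%.

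**Inputs for the count.**

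- N = 120: planned ITT size, SAP 4.2.
- Response rate 50%: an assumption. SAP 4.2 says "the anticipated EASI-75 response rate is approximately 50" per cent, but that is for EASI-75. No rate is given for the threshold endpoints.
- n, the number in the endpoint's denominator: not given. The values below are assumed.

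**Formulas.** Count under the literal rule = round(rate × N). Count on the endpoint's own denominator = round(rate × n). The overstatement factor is N/n.

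| n (share of 120) | N/n | Literal rule | Own denominator | Excess |
|---|---|---|---|---|
| 120 (100%) | 1.00 | 60 | 60 | 0 |
| 114 (95%) | 1.05 | 60 | 57 | 3 |
| 108 (90%) | 1.11 | 60 | 54 | 6 |
| 96 (80%) | 1.25 | 60 | 48 | 12 |
| 84 (70%) | 1.43 | 60 | 42 | 18 |

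The factor does not depend on the rate, but the excess does. With n = 96, a 30% rate gives 36 against 29, and a 60% rate gives 72 against 58.

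**Lower limit.** With n = 119, rounding hides the difference at 50%: 0.50 × 119 = 59.5, which rounds to 60.

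**DLQI age limit alone.** About 12 adolescents are planned, and those aged 16 or 17 complete the DLQI. Age therefore removes at most about 12 of 120, a factor of at most 120/108 = 1.11. The DLQI threshold of 4 would add to this.

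**Week 24.** The same factor applies, with N the Treatment Period II size. That size is not stated, so no count can be given.

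**The case against.** The strongest reply is that the SAP never says the multiplier is the full population. The rule follows five endpoint definitions that each name a restricted group, and Protocol 9.3.3 confines threshold analyses to that group. Table KGBO.5.1 assigns ITT and Treatment Period II only as defaults that other text may override. A programmer who takes the phrase to mean the participants analysed for that endpoint gets the right count, with no error at all.

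This reading is plausible, and it means that a miscount is not certain. It does not settle the matter. Protocol 9.3.3 fixes the denominator of the percentage; it does not state the multiplier. The SAP's sentence uses a term defined elsewhere in the same document, and that definition contains no threshold subset. The SAP does not say which reading applies.

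Three stronger conclusions that a reader might draw are not supported:

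- *Every threshold endpoint will report too many responders.* There is no excess if all participants meet the threshold, and rounding can absorb a shortfall of one.
- *The tables will imply inflated response rates, such as 60/84 = 71%.* That needs the subset printed as N while the full population is the multiplier, and no section prescribes this. If 120 is printed, 60/120 = 50%, which is the correct rate beside a wrong count.
- *Disagreement with the as-observed and LOCF tables would show the error.* Those analyses handle missing data differently by design, so their counts may differ anyway.

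The reply is also right that the stakes are low. The analyses are supportive and descriptive, and no test or decision rests on the count.

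**Conclusion.** The point holds as a minor one. As written, the rule overstates the MCMC-MI responder count by N/n for the five baseline-restricted secondary endpoints whenever some participants fall outside the denominator. Under the assumptions of N = 120 and a 50% response, the excess is 6, 12 or 18 responders for 108, 96 or 84 eligible. The true shares are not in the documents, and under the subset reading the excess is zero.

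Only the derived count is affected. The pooled percentage, its standard error and the 90% bounds are obtained before the multiplication. As-observed and LOCF results do not use the rule. EASI-75, EASI-90 and IGA have no baseline-subset denominator, so the rule is right for them.

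**What to change.** Replace the sentence in SAP 5.4.3 with one to this effect: the number of responders is the pooled percentage multiplied by the number of participants in the ITT or Treatment Period II population (by treatment group where results are reported by group) who are in that endpoint's denominator, rounded to the nearest integer. For the threshold endpoints, that means the baseline threshold is met and, for DLQI, age is 16 or over at baseline. Print the same number as N beside the count.

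The cost is one sentence in the SAP and one denominator in the table program. No estimate changes, and the wording is correct whichever reading was intended.
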